1.3 Rationale for the Proposed Study

The proposed prospective trial will evaluate the utility of topical tranexamic acid in decreasing hematoma, seroma, and ecchymosis in post-mastectomy breast reconstruction patients. We currently use several topical intraoperative hemostatic agents including Arista, Surgicell, and Teseal. These have varying efficacy, inconsistent data, and greater cost than TXA which is produced in many generic formulations. Given that prior literature demonstrates TXA is effective in improving hematoma and bleeding outcomes with no proven risk, especially when applied topically, our goal is to investigate the potential of topical TXA to decrease rates of post-operative bleeding, hematoma, seroma, drain volume, and bruising. This work is significant because TXA offers a cheaper, time-efficient, and simple way to potentially improve outcomes post-mastectomy. Each patient will serve as their own internal control by design, there is no greater risk to any one patient in the study over others. Additionally, if we find that TXA helps with post-operative outcomes and offers a cheaper alternative to various other hemostatic agents on the market, this benefits the hospital and patient.

1.4 Rationale for the TXA Dose Selection/Regimen

Each patient will have one breast exposed to TXA and the other to saline. Prior literature has safely demonstrated the topical application of 1 gram of TXA in patients

undergoing joint replacement surgery[12]. TXA is readily available in the anesthesia cart of the operating room in a sterile, single-dose 1g/ml vial that needs to be reconstituted in 1ml of saline. This can then be added to 40ml of 0.9% normal saline to dilute it to 25mg/ml TXA solution. 20cc of this can then be infiltrated into the breast pocket, which would only expose the patient to 500mg of TXA to that side. With prior evidence to suggest 1 gram of TXA is safe, we are well within the range of TXA that can be safely administered. Additionally, this 20cc of solution can easily fit into a breast pocket without leaking and/or affecting skin closure. 20cc of 25mg/ml solution was also previously described in the small trial by Ausen et al and serves as the model for this study design[15].

There will only be one application of topical TXA and this will be administered intraoperatively, without subjecting patients in theory to systemic risks.

2 Study Objectives

2.1 Hypothesis

Given the use of topical tranexamic acid in reducing bleeding and bruising in other surgical specialties, we believe that topical tranexamic acid can improve post-operative outcomes after breast cancer surgery in a cost-effective manner. We hypothesize that the use of topical TXA in the breast pocket prior to closure will lead to a significantly lower rate of breast hematoma or seroma requiring intervention, decrease overall drain output, and decrease subjective bruising when compared to the control breasts.

2.2 Primary Objective and Endpoint(s)

The primary objective of this study is to evaluate the impact of topical TXA versus control (saline) on key post-operative outcome measures. These include hematoma, seroma, drain output, drain duration, bruising, and reoperation.

Primary Objective	Endpoint(s)	Time Frame
1. To evaluate the impact of TXA on hematoma rates compared to control	Presence of hematoma in 30 day period	From application in the operating room to 30 days of follow up
2. To evaluate the impact of TXA on seroma rates compared to control	Presence of seroma in 3 month period	From application in the operating room to 3 months of follow up

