The Impact of Topical Tranexamic Acid in Breast Reconstruction

Protocol Number: CC # 228012

Investigational Product(s): Topical Tranexamic Acid

Version Number: v4

Version Date: 1/26/24

[figure not shown]
IND Number: N/A

NCT Number: 05807074

Principal Investigator (Sponsor-Investigator)

[name]

University of California, San Francisco

Statistician

[name]

UCSF Surgery Biostatistics Core

Revision History

Version 2 08/12/2022

Version 3 09/27/2022

Protocol Signature Page

1. I agree to follow this protocol version as approved by the UCSF Protocol Review and Monitoring Committee (PRMC), Institutional Review Board (IRB), and Data and Safety Monitoring Committee (DSMC).
2. I will conduct the study in accordance with the International Council for Harmonisation of Technical Requirements for Pharmaceuticals for Human Use (ICH) Good Clinical Practices (GCP) and the applicable IRB, ethical, federal, state, and local regulatory requirements.
3. I certify that I, and the study staff, have received the required training to conduct this research protocol.
4. I agree to maintain adequate and accurate records in accordance with IRB policies, federal, state and local laws and regulations.

UCSF Principal Investigator

[name]

Printed Name

DocuSigned by:

A redacted signature field, indicated by a black rectangular box with a blue border.

Signature

1/26/2024

Date

Abstract

Title	The impact of topical Tranexamic Acid in reconstructive post-oncologic breast surgery
Study Description	Improvement in bleeding and bruising has been described by using both intravenous and topical off-label applications of Tranexamic Acid (TXA) in many surgical fields. The proposed prospective study will evaluate the utility of topical tranexamic acid in decreasing hematoma and seroma rates, drain output, and ecchymosis in post-mastectomy breast reconstruction patients. This novel use of TXA in breast surgery may provide a simple, cost-effective, and safe way to improve outcomes and satisfaction for our breast cancer patients.
Phase of Study	Phase 2
Investigational Products	Tranexamic Acid (Topical application)
Study population	Female patients > 18 years old undergoing bilateral mastectomy with reconstruction or complex closure
Primary Objective	To investigate whether topical tranexamic acid may impact rates of seroma, hematoma, severe bruising, and drain output in the post-mastectomy reconstructive population

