3.1 Characteristics

We propose a prospective, placebo-control trial looking at the effect of topical tranexamic acid on post-operative bleeding, hematoma, seroma, drain output, and bruising in post-mastectomy breast reconstruction. We will recruit patients undergoing bilateral mastectomy at our institution. Patients will be excluded if they have previous history of bleeding or coagulation disorders. Each patient will serve as their own internal control, with one side receiving saline and the other TXA. During surgery and prior to wound closure, we will moisten the wound surface of one side with 20 cc of dilute TXA 25mg/ml solution, and the contralateral with 20cc of saline. Demographics, cancer details, and surgical characteristics will be collected. Outcomes will we assess include hematoma, seroma, reoperation, drain duration, and degree of ecchymosis will be recorded post-operatively for analysis over a 3-month period. The primary outcome will

be presence of hematoma. Secondary outcomes will include seroma, drain output and duration, ecchymosis, and return to operating room.

The surgeon will mix the TXA solution and pass onto the surgical field (detailed in a later section). After completion of the bilateral mastectomy, the plastic surgeon will perform their portion of the procedure. Immediately prior to final closure, 20ml of 25mg/ml TXA solution will be infiltrated into one breast pocket. 20ml of 0.9% normal saline will be infiltrated into the other breast pocket. No other hemostatic agents will be used. The sidedness of the TXA administration will be documented by the surgery team in our record but kept confidential from the surgery clinic staff to prevent bias at post-operative assessments. The solutions will be allowed to dwell while performing incisional closure, and the solutions will be evacuated by the Jackson-Pratt drain when placed to bulb suction at the end of the case. Post-procedure, each patient will be provided with standard post-operative instructions. They will be followed post-operatively for up to 1 year.

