3.2 Sample Size

The goal enrollment is 150 patients, 300 breasts. Given that the literature cites a hematoma rate of up to 5% in mastectomy patients, if we aim for complete reduction with TXA, we will need at least 150 per group to be adequately powered to detect that difference (alpha 0.05, beta 0.2). However, since complete reduction is not realistic, we will aim to recruit as many as possible but with a minimum goal of 150 patients (150 breasts will receive TXA, 150 breasts will receive saline).

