7.1 Statistical analysis

We will compile an encrypted record of each patient and the study or control solution that was administered to each breast intraoperatively. We will then record data from the condition-specific physical examination at each post-operative clinic visit to track presence of hematoma, presence of seroma, laterality with worse bruising, amount of drain output prior to removal, and number of days with drain prior to removal.

Demographic and surgical details will be collected for each patient. These will include patient demographics (i.e., age, BMI, race, ethnicity), clinical cancer characteristics (i.e., type of cancer, neoadjuvant chemo or radiation, adjuvant chemo or radiation), and post-operative outcomes (i.e., hematoma, seroma, infection, return to the operating room, radiology aspiration or drain placement, clinic aspiration). Results will be analyzed comparing the outcomes of the TXA treated breasts with the Control (Saline) treated breasts using T test for continuous variables, and Chi Squared for categorical variables.

Multivariate regression analysis will also be utilized to assess for the importance of various clinical and demographic factors (BMI, cancer laterality, etc.) on overall outcomes. For ecchymosis, the prevalence of worse ecchymosis with or without TXA will be reported as rated by the provider and patient at post operative visits.

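### Drain output, drain duration, bruising and reoperation sit inside the primary objective in 2.2 (two of them also in the Abstract) but are secondary in 2.3 and/or 3.1, and 7.1 has no rule for which result decides efficacy

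*Combined protocol and SAP*

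**What the plan says.** The primary objective appears in two places, with different contents.

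- Abstract, Primary Objective: to investigate "whether topical tranexamic acid may impact rates of seroma, hematoma, severe bruising, and drain output".
- Section 2.2, text: the objective covers key post-operative outcomes. "These include hematoma, seroma, drain output, drain duration, bruising, and reoperation". The endpoint table beneath lists only hematoma (30 days) and seroma (3 months).

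Elsewhere the same outcomes are secondary.

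- Section 2.3, table: bruising, drain output and drain duration. Reoperation is not listed.
- Section 3.1: hematoma is the primary outcome. "Secondary outcomes will include seroma, drain output and duration, ecchymosis, and return to operating room".

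The hypothesis in 2.1 joins a lower rate of hematoma or seroma needing intervention with the expectation that TXA will "decrease overall drain output, and decrease subjective bruising when compared to the control breasts".

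Section 7.1 compares the two sides "using T test for continuous variables, and Chi Squared for categorical variables". It sets no order of testing, significance level or success rule, and for ecchymosis it plans only to report prevalence. The one error rate in the plan is in the sample-size text (3.2 and Abstract), for hematoma: "alpha 0.05, beta 0.2".

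**The concern.** The labels conflict, and nothing in the analysis section says which one governs. This matters because the outcomes differ greatly in how easily they reach significance. Hematoma is rare: section 3.2 says that "the literature cites a hematoma rate of up to 5% in mastectomy patients", and it concedes that TXA is unlikely to abolish the event. Drain output is continuous and measured on both sides of each patient. A null hematoma result beside a significant drain result is therefore a realistic outcome of this trial. Under 3.1 it is a negative primary outcome. Under the Abstract and the 2.2 text it could be presented as meeting the primary objective. The choice would then be made after the data are seen.

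**Working it through.** **1. Where each outcome is placed** (seroma, whose class also differs between the 2.2 table and 3.1, is a separate matter and is left out)

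| Outcome | Abstract objective | 2.2 text | 2.2 table | 2.3 table | 3.1 |
|---|---|---|---|---|---|
| Hematoma | primary | primary | primary | not listed | primary |
| Drain output | primary | primary | not listed | secondary | secondary |
| Drain duration | not named | primary | not listed | secondary | secondary |
| Bruising | primary (severe) | primary | not listed | secondary | secondary |
| Reoperation | not named | primary | not listed | not listed | secondary |

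**2. The plan's own figure.** Inputs from 3.2: 5% against 0%, alpha 0.05, power 80%, 150 per group.

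- Unpooled variance, two-sided: n = (1.96 + 0.8416)² × (0.05 × 0.95) / 0.05² = 7.849 × 19 = 149.1, so 150.
- Pooled variance, two-sided: 152. Power at 150 is 79.5%.
- One-sided: 118 (unpooled) or 120 (pooled), which does not match.

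The stated 150 reproduces as a two-sided calculation on hematoma alone. The plan does not state sidedness, so two-sided is assumed below.

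**3. How likely is a split result?**

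- Hematoma, assuming TXA halves the rate (5% to 2.5%), 150 per group: null SE = √(2 × 0.0375 × 0.9625 / 150) = 0.02194; alternative SE = √((0.05 × 0.95 + 0.025 × 0.975) / 150) = 0.02189; power = Φ((0.025 − 1.96 × 0.02194) / 0.02189) = Φ(−0.82) = 20.5%.
- Drain output, if analysed as paired (7.1 says only t test): the difference detectable with 80% power is (1.96 + 0.84) / √150 = 0.23 SD of the paired differences.

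**4. Chance of at least one false positive if TXA affects nothing.** Assumptions, none of them in the plan: each outcome is tested at two-sided 0.05, and the test statistics are normal with equal pairwise correlation r. With r = 0 the rate is 1 − 0.95^k in either direction and 1 − 0.975^k in favour of TXA. For r > 0 it was simulated with 1,000,000 draws.

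| Set | Direction | r = 0 | r = 0.5 | r = 0.8 |
|---|---|---|---|---|
| Hematoma + the four (k = 5) | either | 22.6% | 18.4% | 12.7% |
| Hematoma + the four (k = 5) | favours TXA | 11.9% | 9.2% | 6.4% |
| Same, no bruising test (k = 4) | either | 18.5% | 15.6% | 11.4% |
| Same, no bruising test (k = 4) | favours TXA | 9.6% | 7.8% | 5.7% |

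The k = 4 rows are there because 7.1 names no bruising-specific test. The nominal rates are 5% in either direction and 2.5% in favour of TXA.

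**The case against.** The best defence is that the plan does label its endpoints. Section 3.1 names one primary outcome, the 2.2 and 2.3 tables carry primary and secondary headings, and the sample size uses hematoma alone. For the four disputed outcomes, every label given at the level of endpoints or outcomes is secondary. Only the prose of the objectives departs from this, and an objective to investigate or evaluate is not a success rule. This is also a single-site phase 2 trial, where formal multiplicity control over secondary outcomes is often not expected.

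Most of that stands, and it limits the point. Several stronger readings are tempting but not supported:

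- A reader might infer that the plan has no labels or hierarchy at all. It has labels, and they conflict. What is missing is a testing order or success rule.
- A reader might infer that the Abstract promotes all four outcomes. It names two, severe bruising and drain output. Nor does 2.3 demote all four, since reoperation is secondary only in 3.1.
- A reader might infer that a drain result alone would confirm the 2.1 hypothesis. That hypothesis is conjunctive, and its reference to significance attaches to hematoma or seroma.
- A reader might infer that each outcome is planned to be tested at 0.05. That level appears only in the sample-size text.
- A reader might quote the rate for all six outcomes in 2.2 (26.5% under independence). That count includes seroma, which raises a different conflict.

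The defence does not remove the contradiction between the objective as written and the secondary labels. Nor does it supply a rule in 7.1 for settling it once results are known.

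**Conclusion.** The point holds as a conflict of labels with no rule to resolve it. A null hematoma result with a significant drain result could be reported as success under the Abstract and 2.2, or as failure under 3.1. For hematoma plus the four outcomes, the illustrative chance of at least one false positive is about 18% (13-23%), or about 9% (6-12%) in favour of TXA. Without a bruising test it is about 16% (11-18%), or about 8% (6-10%) in favour of TXA. These figures rest on assumed two-sided 0.05 tests and an assumed common correlation of 0.5 (range 0.8 to 0). They show the scale of the ambiguity and are not the error rate of a stated procedure. The sample size of 150 per group is not in error on this point. The text should be corrected before outcomes are compared by side.

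**What to change.** 1. Abstract and 2.2 text: remove drain output, drain duration, bruising and reoperation from the primary objective, leaving them secondary as in 2.3 and 3.1. Add reoperation to the 2.3 table.
2. Section 2.1: state the drain and bruising expectations as secondary hypotheses.
3. Section 7.1: state that the efficacy conclusion rests on hematoma, the primary outcome in 3.1 and the basis of the sample size, at two-sided 0.05. State that drain output, drain duration, bruising and return to the operating room are supportive, reported with estimates and 95% confidence intervals. The class of seroma (2.2 table against 3.1) must be reconciled separately.
4. If formal secondary claims are wanted, test them only if the primary is significant, for example by Holm across the secondaries. An ungated procedure would still allow formal claims after a null primary. A formal bruising claim would also need a named test.

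The cost is wording only, with no new patients, data or procedures, and the sample size is unchanged. The downside is that a significant drain or bruising result alone can no longer be presented as meeting the primary objective. By comparison, keeping hematoma and the four as five primaries under Bonferroni (0.05 / 5 = 0.01 each) would cut hematoma power at 150 per group from 79.5% to 57.9% and need 227 per group for 80%.

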2.3 Secondary Objective(s) and Endpoint(s)

[figure not shown]
Secondary Objective	Endpoint(s)	Time Frame
1. To evaluate the impact of TXA on patient and provider rating of bruising, comparing the TXA side to the control side	
Ecchymosis will be compared between the right and left side at each post operative visit and documented. The observer will be blinded to the laterality of TXA	From application in the operating room to 30 days of follow up
2. To evaluate the impact of TXA on total drain output in the first post operative day	
Total drain output over the life of the drain, compared between control and study groups	From drain placement in the operating room to discharge on POD1
3. To evaluate the impact of TXA on total drain duration	
Total drain duration compared between control and study groups	From drain placement in the operating room to removal of the drain

3 Study Design

3.1 Characteristics

We propose a prospective, placebo-control trial looking at the effect of topical tranexamic acid on post-operative bleeding, hematoma, seroma, drain output, and bruising in post-mastectomy breast reconstruction. We will recruit patients undergoing bilateral mastectomy at our institution. Patients will be excluded if they have previous history of bleeding or coagulation disorders. Each patient will serve as their own internal control, with one side receiving saline and the other TXA. During surgery and prior to wound closure, we will moisten the wound surface of one side with 20 cc of dilute TXA 25mg/ml solution, and the contralateral with 20cc of saline. Demographics, cancer details, and surgical characteristics will be collected. Outcomes will we assess include hematoma, seroma, reoperation, drain duration, and degree of ecchymosis will be recorded post-operatively for analysis over a 3-month period. The primary outcome will

be presence of hematoma. Secondary outcomes will include seroma, drain output and duration, ecchymosis, and return to operating room.

The surgeon will mix the TXA solution and pass onto the surgical field (detailed in a later section). After completion of the bilateral mastectomy, the plastic surgeon will perform their portion of the procedure. Immediately prior to final closure, 20ml of 25mg/ml TXA solution will be infiltrated into one breast pocket. 20ml of 0.9% normal saline will be infiltrated into the other breast pocket. No other hemostatic agents will be used. The sidedness of the TXA administration will be documented by the surgery team in our record but kept confidential from the surgery clinic staff to prevent bias at post-operative assessments. The solutions will be allowed to dwell while performing incisional closure, and the solutions will be evacuated by the Jackson-Pratt drain when placed to bulb suction at the end of the case. Post-procedure, each patient will be provided with standard post-operative instructions. They will be followed post-operatively for up to 1 year.

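### Seroma at 3 months is a numbered primary endpoint in section 2.2 but a secondary outcome in section 3.1; no success rule is stated, and the sample size covers hematoma only

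*Combined protocol and SAP*

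**What the plan says.** **Section 2.2** has a table of primary objectives with two numbered rows. Row 1 is hematoma over 30 days. Row 2 is "To evaluate the impact of TXA on seroma rates compared to control", with the endpoint "Presence of seroma in 3 month period". The lead-in to the table is broader still: "These include hematoma, seroma, drain output, drain duration, bruising, and reoperation".

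**Section 2.3** has three numbered secondary rows: bruising, drain output, and lastly "To evaluate the impact of TXA on total drain duration". Seroma is not among them.

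**Section 3.1** says, in the singular, that the primary outcome will "be presence of hematoma". It continues: "Secondary outcomes will include seroma, drain output and duration, ecchymosis, and return to operating room".

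**Section 3.2**, repeated in the abstract's sample-size row, takes a hematoma rate of up to 5% and complete reduction with TXA, and concludes that "we will need at least 150 per group to be adequately powered to detect that difference (alpha 0.05, beta 0.2". It gives no seroma rate, effect or power.

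**Section 7.1** names the t test, chi-squared test and multivariate regression. It does not identify a primary comparison, a rule for combining two primary endpoints, a testing order or a division of alpha.

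**The concern.** A reader cannot tell from the plan what counts as a positive trial. Suppose hematoma shows no difference and seroma gives p<0.05. Under 3.1 the primary endpoint has failed and seroma is supportive. Under one reading of 2.2 a primary endpoint has succeeded. Both reports could cite the protocol, and the choice could be made after outcomes by side are known.

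The plan states an alpha and a beta, and section 2.1 hypothesizes significantly lower rates, so it intends a formal test. That test needs a defined target. If seroma really is primary, the plan also lacks any statement of how well 150 patients can address it.

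**Working it through.** **Step 1. Status of seroma, place by place.**

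| Place | Status of seroma |
|---|---|
| Abstract, primary objective | Named in the primary objective with hematoma, bruising and drain output |
| Abstract, sample size | Not mentioned; hematoma only |
| 2.2 table | Primary, row 2 |
| 2.3 table | Not listed |
| 3.1 | Secondary |
| 3.2 | Not mentioned; hematoma only |
| 7.1 | An outcome to be compared; no rank given |

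The 2.2 table and 3.1 cannot both be right, and no clause ranks one section above the other.

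**Step 2. Reproduce the plan's sample size.** Inputs from 3.2: p1 = 0.05, p2 = 0, alpha 0.05, power 0.80. Sidedness is not stated; two-sided is what reproduces the figure.

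- Unpooled: n = (1.960 + 0.842)² × (0.05 × 0.95) / 0.05² = 149.1, rounded up to 150 per group.
- Pooled: n = [1.960 × √(2 × 0.025 × 0.975) + 0.842 × √(0.05 × 0.95)]² / 0.05² = 151.9, rounded up to 152 per group.

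The stated 150 is reproduced for hematoma alone, with the whole 0.05 spent on it.

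**Step 3. Familywise error under each possible rule.**

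- Hematoma as sole primary (3.1): 0.05, no inflation.
- Both endpoints required: no inflation. Power falls, but by how much cannot be computed without a seroma rate.
- Either endpoint at 0.05 is enough (assumed; the plan does not say so):
  - Upper bound: 0.05 + 0.05 = 0.10.
  - Independent tests: 1 − 0.95² = 0.0975.
  - Positively correlated two-sided normal tests: 1 − P(|Z1| < 1.96 and |Z2| < 1.96) = 0.091 at correlation 0.5 and 0.070 at 0.9.

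These are nominal figures. With few events, the hematoma test may have a true size below 0.05. Enumerating two independent binomials with n = 150 and a true rate of 5% in each group, the exact size is 0.048 for uncorrected chi-squared and 0.024 for Yates or Fisher. In the second case the either-rule bound is 0.024 + 0.05 = 0.074, even with seroma tested at a full 5%. Section 7.1 does not say which version of chi-squared will be used.

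**Step 4. Cost of splitting alpha.** Using the plan's own independent-group approximation, 5% versus 0%, 150 per group:

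Power = Φ{[0.05 × √150 − z × √(2 × 0.025 × 0.975)] / √(0.05 × 0.95)}

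- alpha 0.05, z = 1.960: (0.6124 − 0.4327) / 0.2179 = 0.824, power 79.5%.
- alpha 0.025, z = 2.241: (0.6124 − 0.4949) / 0.2179 = 0.539, power 70.5%.

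The loss is 9.0 points. Restoring 80% power at 0.025 needs 185 per group by the same pooled formula.

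**Step 5. Does pairing matter?** Each patient is her own control, so the data are paired. With no events on the TXA side, every discordant pair points the same way, and the number of discordant pairs is binomial (150, 0.05).

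- Exact McNemar rejects from 6 pairs at 0.05 (2 × 0.5⁶ = 0.031) and from 7 at 0.025 (2 × 0.5⁷ = 0.016): power 76.6% and 62.7%.
- Uncorrected McNemar rejects from 4 pairs at 0.05. At 0.025, 5 versus 0 gives p = 0.0253 and fails, so 6 are needed: power 94.5% and 76.6%.

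The loss from a split is therefore 9.0 points on the plan's approximation, but about 14 points (exact) or 18 points (uncorrected) for paired tests. No single figure should be quoted until the paired test is fixed.

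**The case against.** The strongest reply is that the plan does point to an answer. Section 3.1 speaks of one primary outcome, and both sample-size statements give all of alpha to hematoma. On that reading the 2.2 table is loose drafting and there is no multiplicity problem. Most of this stands: the weight of the text favours hematoma, and it would be wrong to say that the documents offer no guidance. But favouring is not settling. Row 2 of the 2.2 table is explicit and numbered, and nothing subordinates it to 3.1.

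Two supporting arguments are weaker than they look. The absence of seroma from 2.3 does not prove that it is primary, because that table also omits return to the operating room, which 3.1 calls secondary. Nor do the 2.2 lead-in and the abstract objective create four or six rival primary endpoints. They read as a broad statement of aim, and only the two numbered table rows are set out as endpoints with time frames.

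A reader might also infer that the trial's type I error is about 10%. The documents do not support that, because they state no either rule. Without one, 10% is only a conditional nominal bound.

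A phase 2 label does not remove the point, since the plan sets an alpha and a beta.

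**Conclusion.** The contradiction holds in the current text: 2.2 makes seroma primary, 3.1 makes it secondary, 7.1 supplies no decision rule, and the sample size addresses hematoma alone. The consequence that stands under any reading is that the same data, with hematoma null and seroma p<0.05, could be called a primary success or a failed primary.

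Error inflation depends on an assumption. If either endpoint at 0.05 counts, the nominal bound is 10%, with 9.75% under independence and a bound of about 7.4% if the hematoma test is Yates or Fisher (exact size 0.024 at a 5% rate in both groups). If hematoma is the sole primary, or if both are required, there is none.

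A reader might infer that the figure of 150 is itself wrong. It is not, on its own inputs: it reproduces for hematoma at 5% versus 0%. The gap is that it says nothing about seroma, and seroma power cannot be computed from the documents.

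**What to change.** Before any comparison by treated side is run, give seroma one status in the abstract, 2.2, 2.3, 3.1 and 7.1. The choice is the sponsor's.

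**Option A, which matches 3.1 and the existing sample size.** Make presence of hematoma within 30 days the single primary endpoint, tested at two-sided 0.05. Move seroma at 3 months to the 2.3 table, and align the abstract objective and the 2.2 lead-in. N does not change.

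**Option B, seroma stays co-primary.** State in 7.1 whether success means either or both, or give a testing order. For either, use Holm or Bonferroni at a total of 0.05. Restate power in 3.2 with an assumed seroma rate. A 0.025 split lowers hematoma power from 79.5% to 70.5% on the plan's independent-group approximation. Final power figures should be derived for paired data.

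**Cost.** Either option needs a signed amendment approved by PRMC and the IRB under 8.4. Under option A, seroma no longer counts as primary evidence, and the only primary test then rests on an effect about which 3.2 itself says "since complete reduction is not realistic, we will aim to recruit as many as possible". Under option B, either-success at 0.025 each loses power or needs more patients, and both-success loses power by an amount that depends on the seroma rate assumed.
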